#### 8.3 Inhibitor/Antibody Development

FVIII inhibitory antibody development is considered one of the co-primary objectives of this study. Other antibody results are considered part of the secondary objectives of this study.

Results on inhibitory antibodies to FVIII and binding antibodies to FVIII, PEG-FVIII and PEG (both IgG and IgM) and anti-CHO antibodies are to be obtained from the central laboratory.

A subject is to be considered to have developed inhibitory antibodies to FVIII if the result obtained from the central laboratory are  $\geq 0.6~\mathrm{BU}$ .

For the purpose of analyses, positive is considered to be a worse result than a negative result.

Descriptive statistics and listings on inhibitory antibodies to FVIII and binding antibodies to FVIII, PEG-FVIII and PEG and anti-CHO antibodies are to be presented for the SAS. Summaries are to be presented by age categories.

The proportion of subjects which developed inhibitory antibodies to FVIII at any time during the study is to be reported, together with exact Clopper-Pearson 95% confidence intervals for the proportion. The subset of subjects included in this analysis are:

- Subjects that developed inhibitory antibodies to FVIII at any time during the study; and
- Subjects that did not develop any inhibitory antibodies to FVIII but had 100 or more EDs to BAX 855 across all BAX 855 studies AND had a FVIII inhibitory antibody test result from the central laboratory after the 100th ED.

The SAS® code to be used in the Clopper-Pearson analysis:

```
PROC FREQ DATA = <ds>;
  WEIGHT <count>;
  TABLES <result> / BINOMIAL (EXACT CP) ALPHA = 0.05 CL;
RUN;
QUIT;
```

where <ds> refers to the input dataset, <count> the number of subjects with particular result and <result> to the actual result, i.e., "Yes" or "No".

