8.7.3.6 Immune Tolerance Induction for Inhibitor Development

Subjects who develop a confirmed (ie, 2 separate assessments within a 2 to 4 week period from the central laboratory) high responder inhibitor (>5 BU) or low responder inhibitor (≤ 5 BU but ≥ 0.6 BU) that cannot be adequately managed by the protocol-required prophylactic regimen with BAX 855 will be discontinued from this continuation study. The decision to initiate immune tolerance induction (ITI) (ITI) with ADVATE will be made by the subject's physician, and may be discussed with the sponsor's medical director prior to initiation. The regimen used for ITI will be determined by the treating physician but must be approved by the sponsor's medical director. ITI is not within the scope of this study.

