9.2 Exclusion Criteria

9.2.1 Subjects Transitioning from Other BAX 855 Studies

Subjects transitioning from other BAX 855 studies who meet **ANY** of the following criteria are not eligible for this study:

1. Subject had detectable FVIII inhibitory antibodies (≥ 0.6 BU using the Nijmegen modification of the Bethesda assay) as confirmed by central laboratory at screening.
2. Subject has developed FVIII inhibitory antibodies (≥ 0.6 BU using the Nijmegen modification of the Bethesda assay as determined at central laboratory in a previous BAX 855 study).
3. Subject has acquired a hemostatic defect other than hemophilia A (eg, qualitative platelet defect or von Willebrand's disease) in a previous BAX 855 study.

ix If FVIII activity is $\geq 1\%$, severe hemophilia A classification can be confirmed by historically documented FVIII clotting activity < 1% performed by a certified clinical laboratory or by a documented genotype known to result in severe hemophilia A.

4. Subject has severe chronic hepatic dysfunction (eg, ≥ 5 times upper limit of normal alanine aminotransferase [ALT], as confirmed by central laboratory at screening).
5. Subject has severe renal impairment (serum creatinine > 2.0 mg/dL), as confirmed by central laboratory at screening.
6. Subject experienced a life-threatening or gastrointestinal bleeding episode within 3 months prior to study entry.
7. Subject is scheduled to use other PEGylated drugs during study participation.
8. Subject is planning to take part in any other clinical study during the course of the continuation study, with the exception of any other parallel BAX 855 study.
9. Subject has medical, psychiatric, or cognitive illness or recreational drug/alcohol use that, in the opinion of the investigator, would affect subject safety or compliance.
10. Subject is a family member or employee of the investigator.

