12.7.6 Immunogenicity Assays

The primary study and safety assessment is the immunogenicity of BAX 855 which will be assessed by measurement of the following antibodies:

- Inhibitory antibodies to FVIII – measured by the Nijmegen modification of the Bethesda assay
- Binding antibodies to FVIII, BAX 855, and PEG. Both IgG and IgM antibodies will be measured using an ELISA assay.
- Anti-CHO antibodies

To avoid an impact of residual FVIII in plasma, subjects must undergo washout period of at least 84 to preferably 96 hours following the last BAX 855 infusion or at least 72 hours following the last infusion with another FVIII concentrate at the screening, follow-up and end of study visits, as well as prior to a potential unscheduled test. Additionally, the subject should be in a non-bleeding state.

A low titer (responder) inhibitor is defined as ≤ 5 BU but ≥ 0.6 BU. A high titer (responder) inhibitor is defined as > 5 BU by Nijmegen modification of the Bethesda assay. Inhibitors must be confirmed by 2 separate assessments within a 2 to 4 week period from the central laboratory.

Inhibitory antibodies to FVIII will be measured using the Nijmegen modification of the Bethesda inhibitor assay.

^{xviii} Note: Measurement of TGA parameters is optional in subjects on fixed dose prophylactic treatment regimen and subjects aged < 12 years on PK-tailored prophylactic treatment regimen.

Binding antibodies (IgG and IgM) to FVIII and BAX 855, as well as to PEG, will be measured routinely using ELISA. Based on the variability of these tests, only samples with titers $\geq 1:80$ can be confirmed and will be evaluated as positive. Furthermore, only increases of more than 2 titer steps between pre- and post-treatment samples will be considered positive for treatment-related antibody development. IgG subclass 1-4, IgA (using ELISA) and IgE antibodies (using ImmunoCaps, Phadia) may be assessed as clinically indicated.

The assay for antibodies to CHO protein will use CHO protein derived from cultures of untransfected cells. Testing for binding of anti-CHO protein antibodies will be performed on citrate-anti-coagulated plasma using an ELISA employing polyclonal anti-human IgG antibodies. Antibody-containing samples will be identified in a screening assay followed by a confirmatory assay to exclude false positive results.

Details on the sampling of blood for these assessments are presented in Supplement [20.3](#) and Supplement [20.4](#).

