13.4 Methods of Analysis

13.4.1 Primary Outcome Measure

13.4.1.1 Primary Safety Outcome Measure

The number and proportion (Clopper-Pearson exact 95% CI) of subjects having been exposed to BAX 855 who develop inhibitory antibodies to FVIII (≥ 0.6 BU) will be provided.

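### SAP 8.3 counts any single FVIII inhibitor result of 0.6 BU or more as a co-primary event, without the confirmation that Protocol 12.7.6 requires

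*SAP*

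**What the plan says.** **Protocol, analysis.** Section 13.4.1.1 and the synopsis ask for the number and proportion, with an exact interval, of "subjects having been exposed to BAX 855 who develop inhibitory antibodies to FVIII". The threshold of 0.6 BU follows in brackets. Confirmation is not mentioned.

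**Protocol, assay.** Section 12.7.6 opens by naming immunogenicity as the primary safety assessment, sets the low-titer and high-titer bands, and then adds: "Inhibitors must be confirmed by 2 separate assessments within a 2 to 4 week period from the central laboratory". The sentence is not limited to any one use of the result.

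**Protocol, other uses.** Section 8.7.3.6 applies to "Subjects who develop a confirmed (ie, 2 separate assessments within a 2 to 4 week period from the central laboratory". Section 12.1.1.1 lists a confirmed inhibitor of 0.6 BU or more among the medically important SAEs.

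**SAP.** Section 8.3 gives the operative derivation: "A subject is to be considered to have developed inhibitory antibodies to FVIII if the result obtained from the central laboratory are" 0.6 BU or more. It continues: "The proportion of subjects which developed inhibitory antibodies to FVIII at any time during the study is to be reported", with Clopper-Pearson limits. It also says that, for analysis, a positive ranks as worse than a negative. Two kinds of subject enter the analysis. The first is anyone who developed an inhibitor. The second is anyone who did not, reached 100 exposure days (EDs), and "had a FVIII inhibitory antibody test result from the central laboratory after the" 100th ED.

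**The concern.** The inhibitor proportion is the co-primary safety result. The protocol treats an inhibitor as something established by repeat testing, but the SAP counts it from one result. A programmer following SAP 8.3 has no instruction that lets a negative repeat cancel an earlier positive, and the ranking rule points the other way.

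Two things are at stake. A refuted positive would inflate the estimate and its upper limit. It would also not meet the SAE definition, so one study report could show an inhibitor case in the co-primary table that is missing from the SAE table, with no rule to reconcile them.

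In the same section the protocol guards the other antibodies against false positives: binding antibodies count only from a titer of 1:80, and anti-CHO positives go through a confirmatory assay. In the SAP derivation the co-primary antibody has no such guard.

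**Working it through.** **1. The passages side by side**

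- Protocol 12.7.6: threshold 0.6 BU; confirmation by 2 central-laboratory assessments within 2 to 4 weeks is required.
- Protocol 13.4.1.1 and synopsis: threshold 0.6 BU; silent on confirmation.
- Protocol 8.7.3.6 (discontinuation) and 12.1.1.1 (SAE): confirmed inhibitor.
- SAP 8.3: threshold 0.6 BU; any central-laboratory result; positive outranks negative; no confirmation step.

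Take a subject with 0.6 BU or more at one visit and a negative repeat within 2 to 4 weeks. Under 12.7.6 the inhibitor is not confirmed. Under 12.1.1.1 it is not an SAE on that criterion. Under SAP 8.3 the subject is an event.

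**2. Effect on the reported interval**

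Inputs: 200 evaluable subjects and about 250 enrolled (Protocol 13.1, SAP 2.3); two-sided 95% Clopper-Pearson limits (SAP 8.3). The plan states no expected incidence or target precision, so it has no figure of its own to reproduce here.

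The upper limit U for x events in N subjects solves P(X ≤ x | N, U) = 0.025. For x = 0 this is U = 1 − 0.025^(1/N); at N = 200, U = 1 − 0.025^(1/200) = 1.83%. For x ≥ 1, U is the 0.975 quantile of Beta(x + 1, N − x).

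| Events | N = 200: estimate, upper limit | N = 250: estimate, upper limit |
|---|---|---|
| 0 | 0.0%, 1.83% | 0.0%, 1.46% |
| 1 | 0.5%, 2.75% | 0.4%, 2.21% |
| 2 | 1.0%, 3.57% | 0.8%, 2.86% |

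If the only positive is refuted, the upper limit under the SAP rule is 2.75 / 1.83 = 1.5 times what it would be with confirmation (N = 200). If that subject also lacks 100 EDs or a test after the 100th ED, he leaves the analysis once the positive is set aside. The result is then 0/199, with upper limit 1 − 0.025^(1/199) = 1.84%.

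**3. How likely is a refuted positive? (illustration only)**

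The documents give no false-positive rate for the assay. Assume a rate f per test and independent errors. On the fixed-dose schedule, 3 months of participation gives 2 post-baseline tests (6 weeks, end of study). Twelve months gives 5 (6 weeks; 3, 6 and 9 months; end of study). For 200 subjects that is T = 400 to 1,000 tests, and P(at least one) = 1 − (1 − f)^T.

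- f = 0.05%: 18.1% (T = 400) to 39.4% (T = 1,000).
- f = 0.1%: 33.0% to 63.2%.

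The point does not depend on these values.

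**The case against.** **The single-result rule is cautious and follows the protocol's literal wording.** For a safety endpoint, counting every positive errs on the safe side, and the ranking of positive over negative looks like a deliberate worst-case convention. SAP 8.3 does match the wording of 13.4.1.1, so its absence from the list of changes in SAP 5.7 is not in itself an error. That stands. But caution does not explain why the mandatory sentence in 12.7.6 has no place in the derivation of the endpoint that section covers. Keeping the single-result rule as a sensitivity analysis preserves the cautious figure.

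**The harm is limited.** There is no hypothesis or decision threshold, SAP 8.2 and 8.3 already list the results, and at very low counts a reader could find the case and recalculate. This stands, and it bounds the severity. A listing still does not remove a refuted positive from the co-primary estimate. The SAE count serves a different purpose, so a difference between the two is not an error in itself; the gap is that nothing in the plan explains it.

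**Unseen documents.** The laboratory manual and the Output Templates could affect how results are released or flagged. They are not available here and would not change the text of SAP 8.3.

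**A stronger reading to avoid.** A reader might infer that the protocol holds two rival definitions, with 13.4.1.1 meaning 0.6 BU alone, and might cite exclusion criterion 2 in 9.2.1 ("Subject has developed FVIII inhibitory antibodies") as a single-result rule. The documents do not support this. Section 13.4.1.1 does not exclude confirmation; it leaves it unmentioned. The protocol uses the same shorthand elsewhere: 8.2 gives the discontinuation rule for inhibitors without the word confirmed, and 8.7.3.6 gives it with the word. Criterion 2 refers to a central-laboratory determination in a previous study and does not say that one result is enough. On the protocol side the gap is one of omission.

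**Conclusion.** The concern holds against SAP 8.3. The protocol's analysis section can be read consistently with 12.7.6; the SAP derivation cannot, because it counts any central-laboratory result of 0.6 BU or more and gives a negative repeat no effect. This is a wrong rule, not merely missing detail.

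Each refuted positive adds 0.5 percentage points to the estimate at N = 200, and the first adds 2.75 − 1.83 = 0.92 points to the upper limit. The bias has one direction, towards overstating incidence. The size rests on the planned N and on a refuted positive actually occurring. How often that happens cannot be judged from the documents. The change should be made before the co-primary result is produced, because choosing the definition after seeing the cases would be post hoc.

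**What to change.** In SAP 8.3:

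- Define the primary event as a post-baseline result of 0.6 BU or more, confirmed as in Protocol 12.7.6. State whether the first positive is one of the two assessments.
- Count a positive with no valid repeat as an event, so that a missing sample cannot lower the estimate.
- Judge a subject whose positive is refuted under the second bullet of SAP 8.3 (at least 100 EDs and a test after the 100th).
- Report the single-result rule as a sensitivity analysis, and flag unconfirmed positives in the listings already planned.

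In Protocol 13.4.1.1 and the synopsis, add a cross-reference to 12.7.6.

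The cost is a few SAP sentences, one sensitivity row, one listing flag and two cross-references. No new type of testing is needed, because the protocol already requires confirmation. One limit remains: a first positive at the end-of-study visit has no later scheduled visit, so its repeat depends on the extra sampling that 12.7.6 foresees when it sets the washout "as well as prior to a potential unscheduled test". Where that repeat is not obtained, the positive stays an event under the second item above.

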8.2 Overall Study Design

Subjects who complete treatment and assessments in the other BAX 855 studies and BAX 855-naïve subjects who fulfill the inclusion/exclusion criteria will be eligible to participate in this continuation study. Approximately 250 PTPs with severe hemophilia A will be enrolled to achieve 200 evaluable subjects. This study was designed to be in compliance with EMA/CHMP/BPWP/144533/2009⁶ recommendations for the study of FVIII in severe hemophilia A.

The subject's hemophilia history, bleeding episode history, and FVIII usage and treatment regimen(s) within the previous year will be collected at screening for BAX 855 naïve subjects. Results of the screening assessments will be used to establish subject's eligibility for this study and may serve as baseline measurements. Subjects transitioning from the other BAX 855 studies may use end of study assessments in their prior study for screening assessments in this continuation study.

Once eligibility is established, subjects can choose to receive either a fixed BAX 855 prophylaxis or a PK-tailored BAX 855 prophylaxis (as described in Section 8.7.3). Subjects will also treat breakthrough bleeding episodes with BAX 855. Details on bleeding episodes, the number of infusions used for treatment, and the efficacy of treatment (based on a 4-point rating scale; see Section 11.2) will be recorded in an electronic diary (e-diary). Subjects will be treated with BAX 855 for a minimum of 100 EDs (accumulated across all BAX 855 studies they have participated in).

Transitioning subjects receiving a fixed dose prophylactic treatment regimen will return to the study site at 6 weeks following screening to confirm eligibility and at this visit and subsequent visits every 3 months following screening, IR will be determined, efficacy and safety will be assessed and e-diary will be reviewed. BAX855 naïve subjects with

confirmed eligibility will undergo their baseline visit for determination of IR at exposure day 1 (ED1) and return to the study site after 6 weeks and every 3 months following their baseline visit for IR determination, efficacy and safety assessment and e-diary review.

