10.3.1 Subjects Transitioning from Other BAX 855 Studies

Subjects transitioning from other BAX 855 studies can use the end of study assessments in their previous BAX 855 study for screening visit assessments in this continuation study. Any additional required screening assessments will be performed the same day. Subjects will return to the study site no later than 6 (\pm 1) weeks after the end of study visit in their prior study/continuation study's screening visit to confirm eligibility.

Additionally, transitioning subjects will receive IP treatment either as part of the IR determination of the end of study visit of the previous BAX855 study or the first IP treatment will be given at the screening visit of this continuation study to subjects transitioning from other BAX 855 studies.

Transitioning subjects^x who decide to receive a PK-tailored treatment regimen will continue receiving their study-specific treatment regimen with BAX 855^{xi} (eg, twice weekly 45 ± 5 IU/kg) until baseline/start of PK-tailored prophylaxis. The study-specific prophylactic treatment regimen will be interrupted by one infusion for PK determination in those subjects for whom PK is not yet available.

x As well as subjects who are already participating in the continuation study.

xi NOTE: This refers to the type of treatment that subjects will receive with BAX 855 from this continuation study (not from the previous BAX 855 study).

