## 4.2 Safety Analysis Set (SAS)

The safety analysis set (SAS) is to comprise all subjects in the ENR with at least one BAX 855 infusion. All safety analyses are to be performed on the SAS.

Information on dosing with BAX 855 is to be obtained from the following eCRF panels:

- Study Infusion eCRF panels.
- *Infusion for Determination of Incremental Recovery* eCRF panels.
- Infusion for PK Assessment eCRF panels.
- *Minor Surgery* eCRF panels.

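### SAP 8.3 sets no negative-baseline condition for a developed FVIII inhibitor, so an inhibitor present before the first BAX 855 infusion in this study can enter the co-primary safety proportion

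*SAP*

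**What the plan says.** **The event.** Protocol 13.4.1.1 asks for "The number and proportion (Clopper-Pearson exact 95% CI) of subjects having been exposed to BAX 855" who develop FVIII inhibitors at 0.6 BU or more. SAP 8.3 makes this operational: "A subject is to be considered to have developed inhibitory antibodies to FVIII if the result obtained from the central laboratory are" at or above 0.6 BU. No earlier negative result, post-infusion sample or repeat test is required.

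**Who is analysed.** SAP 8.3 admits two groups. The first is "Subjects that developed inhibitory antibodies to FVIII at any time during the study; and" the second begins "Subjects that did not develop any inhibitory antibodies to FVIII but had 100 or more EDs to BAX 855 across all BAX 855 studies" and must also have a central inhibitor test after the 100th exposure day (ED). Positives need neither the EDs nor the late test. The safety analysis set (SAP 4.2) is "all subjects in the ENR with at least one BAX 855 infusion", with no eligibility condition.

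**Transitioning subjects.** Exclusion criterion 1 (Protocol 9.2.1) applies where "Subject had detectable FVIII inhibitory antibodies" at 0.6 BU or more, by central laboratory, at screening. The screening visit is the parent study's end-of-study visit, and the inhibitor result is transcribed from it (Protocol 20.2.1.1.1 and 20.2.2.1.1). Under Protocol 10.3.1, either the incremental recovery infusion at that end-of-study visit serves as the first treatment, or "the first IP treatment will be given at the screening visit of this continuation study". Product to continue treatment is also dispensed then. On the fixed-dose regimen, Protocol 8.2 says these subjects "will return to the study site at 6 weeks following screening to confirm eligibility". On the PK-tailored regimen, confirmation is at the PK assessment or the baseline visit.

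**Naïve subjects.** Immunogenicity is sampled within 30 minutes before the first BAX 855 infusion, at ED1 or at the PK assessment. This can be up to 45 days after screening, while the subject is still using another FVIII product.

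**The concern.** The co-primary objective is the incidence of inhibitor development. A development endpoint needs a starting state, and SAP 8.3 gives none. SAP 5.5 does define a baseline, treats a sample from the day of first infusion as baseline, and allows parent-study results to serve when nothing else is available. SAP 8.3 does not use it.

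The neighbouring rules are stricter. SAP 8.1 limits adverse events to those starting at or after the first BAX 855 administration in this study. Protocol 12.7.6 requires an increase from the pre-treatment to the post-treatment sample before a binding antibody is called treatment-related. The same section requires an inhibitor to be confirmed by two separate central-laboratory assessments within 2 to 4 weeks, and SAP 8.3 omits that too.

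Two things are at stake. For a naïve subject, an inhibitor that arose on another FVIII product could be reported as developed on BAX 855. For a transitioning subject, the inhibitor found in the parent study's last sample could be counted in both studies. In either case the subject reaches the numerator after as little as one infusion in this study.

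**Working it through.** **Step 1. Is the subject in the analysis population?** A transitioning subject has consented and been infused at the screening visit, or has been given product there to continue treatment. One infusion in this study meets SAP 4.2, and later ineligibility does not remove the subject.

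**Step 2. Which samples can trigger the event?**

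| Sample | SAP 5.5 status | Counted under SAP 8.3? |
|---|---|---|
| Transitioning: screening sample, transcribed from the parent study | Baseline | Depends on whether it falls within the study, which is not defined |
| Naïve: pre-infusion sample at ED1 or PK assessment | Baseline (same date as first infusion) | Depends on the same reading |
| Transitioning: same inhibitor still positive at week 6 or at termination | Post-baseline | Yes |

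For the third row, Protocol 20.4.1 schedules immunogenicity at week 6 and at the end-of-study visit, and the latter also covers withdrawal and discontinuation. A subject found ineligible may therefore still supply a post-infusion positive.

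**Step 3. Size.** The plan has no figure to reproduce. The approximately 250 enrolled and 200 evaluable follow a guideline, with no expected inhibitor rate and no precision target. As an illustration, assume 200 negatives who meet the 100-ED and late-test conditions, no new inhibitors, and *k* pre-existing positives that are counted. SAP 8.3 adds each positive to numerator and denominator, so the proportion is *k*/(200 + *k*).

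Exact Clopper-Pearson limits for *x* of *n*:
- lower = Beta quantile at 0.025 with parameters (*x*, *n* − *x* + 1), or 0 if *x* = 0;
- upper = Beta quantile at 0.975 with parameters (*x* + 1, *n* − *x*).

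For 0/200 the upper limit reduces to 1 − 0.025^(1/200) = 1.83%.

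| *k* (assumed) | Result | 95% CI |
|---|---|---|
| 0 | 0/200 = 0.00% | 0.00 to 1.83% |
| 1 | 1/201 = 0.50% | 0.01 to 2.74% |
| 2 | 2/202 = 0.99% | 0.12 to 3.53% |
| 3 | 3/203 = 1.48% | 0.31 to 4.26% |

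One case raises the upper limit by a factor of 2.74/1.83 = 1.50. If one true new inhibitor is present among 200 analysed subjects, one pre-existing case moves 1/200 (0.50%, 0.01 to 2.75%) to 2/201 (1.00%, 0.12 to 3.55%).

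**The case against.** A reader might infer that every inhibitor present at entry becomes a co-primary event. The documents do not support that. The endpoint concerns subjects who develop inhibitors after exposure, SAP 5.3 sets Day 1 at the first infusion in this study, and SAP 5.5 would class the screening and same-day pre-infusion samples as baseline. A programmer could reasonably leave them out. This stands for those samples. It does not help with a positive that persists to a later visit, which meets the SAP 8.3 rule as written.

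A reader might also take it as stated that the inhibitor result is unknown at infusion. It is not stated. For transitioning subjects on the fixed-dose regimen, eligibility assessment is listed among the pre-infusion procedures at screening, and no laboratory turnaround time is given. That the result is missing is an inference from same-day central-laboratory sampling and from the later confirmation visit.

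The exclusions are strong. Transitioning subjects with an inhibitor in a previous BAX 855 study are barred by exclusion criterion 2. Naïve subjects must be negative at screening, have no inhibitor history, and have at least 150 prior EDs (50 if under 6 years). Few cases should arise.

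Finally, a transitioning subject's inhibitor followed BAX 855 exposure in the parent study, so counting it risks duplication rather than attribution to the wrong product. Because negatives qualify on EDs from all BAX 855 studies, simply deleting such a case would lower a cumulative estimate and hide it. This objection stands and shapes the remedy. Listings for the safety analysis set, and the reporting of confirmed inhibitors as serious adverse events (Protocol 12.1.1.1), would leave a trace of each case but would not correct the headline proportion.

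**Conclusion.** The gap is real and narrow. SAP 8.3 has no baseline condition. A pre-infusion positive can therefore be counted on one reading of the study period, and a screening inhibitor that persists to a post-infusion sample in a transitioning subject is counted on any reading. The number affected is unknown and probably very small. The figures assume 200 qualifying negatives and no new inhibitors: one case gives 0.50% with an upper limit of 2.74% in place of 0% with 1.83%, and two give 0.99% with 3.53%. The point is worth correcting because the protocol (6.5) regards inhibitor risk in previously treated patients as low, so a single case can decide the headline. It does not show that such cases occurred or that the reported proportion is wrong.

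**What to change.** In SAP 8.3, define the event as a central-laboratory result of 0.6 BU or more that is:

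- confirmed as Protocol 12.7.6 requires;
- from a sample drawn after the first BAX 855 infusion in this study;
- in a subject whose SAP 5.5 baseline result was below 0.6 BU.

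Leave baseline positives out of the numerator and denominator of the main proportion, and list them separately with their parent study. Because parent-study EDs count toward the 100, also report a sensitivity proportion that includes transitioning baseline positives, so that no inhibitor that followed BAX 855 exposure is hidden. List positives that lack a confirmatory sample.

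Protocol 8.2, Protocol 10.3.1 and exclusion criterion 1 should be reconciled on the order of screening infusion, inhibitor result and eligibility confirmation.

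The cost is a short addition to SAP 8.3, one listing and one extra proportion, using results and infusion records the study already collects. The downside is a slightly smaller numerator and denominator in the main proportion.
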